5.1 Duration of the Study

The duration of the study for each subject is approximately 17 weeks (up to 35 days screening and 12 weeks treatment).

5.2 Study Population and Number of Subjects

Approximately 700 subjects, \geq 9 years of age, with acne vulgaris on the face, will be enrolled.

5.3 Selection of Subjects

Subject selection criteria are outlined below. Any questions on the eligibility of a subject for this study must be referred to the Sponsor or their designee, prior to enrollment. No exceptions to inclusion or exclusion criteria will be made.

5.3.1 Inclusion Criteria

Subjects must meet all of the following criteria to be eligible for study participation:

- 1. Signed informed consent and, for subjects under legal adult age, signed assent
- 2. Age ≥ 9 years
- 3. Willing to comply with the protocol. Subjects under legal adult age will be assessed by the investigator as to their ability to comply with the protocol
- 4. Male or non-pregnant (negative serum pregnancy test at screening for female subjects of child-bearing potential), non-lactating females
- 5. In the case of females of childbearing potential), are using an acceptable form of birth control (Section 5.3.4)
- 6. In the case of females of childbearing potential, have a negative urine pregnancy test at Baseline/Day 1
- 7. Clinical diagnosis of facial acne vulgaris defined as:
 - At least 20 inflammatory lesions, and
 - At least 20 non-inflammatory lesions, and
 - Investigator Global Assessment of 3 or greater
- 8. Willing to refrain from using any treatments for acne vulgaris, other than the investigational product, including topical or systemic antibiotics.

5.3.2 Exclusion Criteria

Subjects meeting any of the following criteria are not eligible for study participation:

1. Previous active treatment in Olumacostat Glasaretil (DRM01B) Gel trials

- 2. Females who are currently pregnant, lactating or planning to become pregnant during the course of the study
- 3. Known hypersensitivity to Olumacostat Glasaretil or its excipients
- 4. Any skin condition which may interfere with the evaluation of safety or, of acne vulgaris (e.g., rosacea; seborrheic dermatitis; perioral dermatitis; corticosteroid-induced acne or folliculitis)
- 5. Excessive facial hair that would interfere with diagnosis or assessment of acne vulgaris
- 6. Excessive sun exposure that could affect the clinical state of acne, in the opinion of the investigator or, anticipated use of tanning booths
- 7. Active cystic acne or acne congoblata, acne fulminans, and secondary acne
- 8. Two or more active nodulocystic lesions on the face
- 9. Screening clinical chemistry, hematology, or urinalysis laboratory value, deemed clinically significant, by the Investigator
- 10. Abnormal findings on screening ECG, deemed clinically significant by the Investigator
- 11. Subjects who are actively participating in an experimental therapy study or who have received experimental therapy within 30 days or 5 half-lives (whichever is longer) of the Baseline visit
- 12. Subjects who are a poor medical risk because of other systemic diseases or active uncontrolled infections, in the opinion of the investigator
- 13. Any other condition which, in the judgment of the investigator, would put the subject at unacceptable risk for participation in the study
- 14. Treatment with over-the-counter topical medications for the treatment of acne vulgaris including benzoyl peroxide, topical anti-inflammatory medications, corticosteroids, α-hydroxy/glycolic acid on the face within 2 weeks prior to Baseline
- 15. Treatment with systemic corticosteroids (use of intranasal and inhaled corticosteroids allowed for seasonal allergies and asthma) within 4 weeks prior to Baseline
- 16. Treatment with systemic antibiotics or systemic anti-acne drugs within 4 weeks prior to Baseline
- 17. Prescription topical retinoid use on the face within 4 weeks prior to Baseline (e.g., tretinoin, tazarotene, adapalene)
- 18. Treatment with a new hormonal therapy or dose change to existing hormonal therapy within 12 weeks prior to Baseline (hormonal therapies include, but are not limited to, estrogenic and progestational agents such as birth control pills).
- 19. Use of androgen receptor blockers (such as spironolactone or flutamide) within 2 weeks prior to Baseline.
- 20. Oral retinoid use (e.g., isotretinoin) within 12 months prior to Baseline or vitamin A supplements greater than 10,000 units/day within 6 months prior to Baseline

21. Facial procedures (chemical or laser peel, microdermabrasion, etc.) within 8 weeks prior to Baseline or if anticipated during the study

5.3.3 Females – Non-childbearing Potential

Female subjects of non-childbearing potential are women 45 years or older and at least 2 years postmenopausal or surgically sterile (e.g., total hysterectomy, bilateral oophorectomy). All other female subjects will be considered to be of childbearing potential.

5.3.4 Females – Childbearing Potential

Pregnancy hormones may cause acne to flare. To avoid confounding the assessment of efficacy pregnancy should be avoided. Acceptable contraceptive methods for sexually active female subjects of childbearing potential include one of the following:

- Abstinence
- Oral/implant/injectable/transdermal contraceptives
- Intrauterine device
- Condom with spermicide
- Diaphragm with spermicide
- Partner vasectomized or
- Tubal ligation

Abstinence or vasectomies are acceptable if the female subject agrees to implement one of the other acceptable methods of birth control if her lifestyle/partner changes. Female subjects of childbearing potential must use acceptable methods of contraception starting from the Screening Visit and throughout the study.

6 STUDY DRUG

6.1 Investigational Medicinal Product

Study medication, will be supplied as Olumacostat Glasaretil Gel, 5.0% and Olumacostat Glasaretil Gel, Vehicle.

Olumacostat Glasaretil Gel is formulated as an alcohol based gel for topical application. Olumacostat Glasaretil Gel, 5.0% contains 50 mg of olumacostat glasaretil per gram of gel, ethanol, isopropanol, polyethylene glycol 400, dimethyl isosorbide and hydroxypropy-cellulose and appears as a translucent, colorless to faintly yellow gel.

Olumacostat Glasaretil Gel, Vehicle has the same appearance and contains the same ingredients as Olumacostat Glasaretil Gel, 5.0%, with the exception of olumacostat glasaretil.

6.2 Packaging, Labeling and Storage

The Olumacostat Glasaretil Gel, 5.0% and Olumacostat Glasaretil Gel, Vehicle gel will be packaged in identical 45g aluminum tubes. Each tube contains approximately 40g of gel.

Study drug for each subject enrolled will be packaged in a study kit. Each kit will contain 6 tubes to allow for 12 weeks of study drug application.

Study drug tubes and kits will be labeled with the study number, a unique kit number, contents, storage conditions, manufacturer and Sponsor information, and precautionary statements and expiry date, if applicable.

Study drug kits are to be stored at room temperature (25°C with allowable excursion to 15-30°C) in a secure, locked facility accessible only to authorized study personnel. Study drug must not be placed in refrigerator or frozen, exposed to heat or stored at high temperatures. This product is flammable. Avoid fire, flame, or smoking during and immediately following application.

6.3 Treatment Assignment

Randomization and IWRS

At the Baseline/Day 1 visit, qualified subjects will be randomized to treatment using an Interactive Web-based Randomization System (IWRS). The IWRS will assign a study drug kit number based on a predetermined randomization schedule. The kit number will be recorded in the electronic case report form (eCRF). Approximately 467 subjects will be randomized to active treatment and approximately 233 subjects will be randomized to vehicle treatment for a total of approximately 700 subjects. Subjects will be randomized to treatment groups in such a manner to balance treatment allocation within study sites in a 2:1 fashion.

Each subject screened will be assigned a unique subject number.

Study Blinding

The Sponsor, the CRO, the Investigator, study site personnel and subjects will be blinded to the treatment assignment.

The integrity of this clinical study must be maintained by observing the treatment blind. If an adverse event occurs which cannot be managed without knowing whether the subject is receiving active study drug or vehicle solution, the IWR system will be used to obtain treatment assignment information. The Medical Monitor must be notified whenever study medication is unblinded, preferably prior to unblinding a subject.

6.4 Study Drug Dispensing and Return

It is the responsibility of the Investigator to ensure that study drug is only used on study subjects enrolled in this study. The study drug must only be dispensed from official study sites by authorized personnel according to the protocol and local regulations.

Study drug will be dispensed by the study site to the subject at each study visit. Two tubes contain enough study drug for 1 month of application. At each visit, the subject will be dispensed enough tubes to allow dosing until the next visit. Partially used tubes may be re-dispensed at the site's discretion.

Subjects are to return all study medication tubes (used and unused) to the study site. Study tubes will be weighed prior to dispensing and upon return. Sites are allowed to re-dispense tubes. If required, tubes will be re-weighed prior to re-dispensing Weights will be recorded in the source documents and eCRF.

Each subject is to be instructed on the importance of returning study drug at the next study visit. If a subject does not return study drug, they will be instructed to return it as soon as possible. The site staff will visually inspect the tube to ensure product usage is consistent with the subject's dosing diary.

6.5 Study Drug Application

Subjects will be instructed on the application of the study medication. The first dose of the study drug will be applied in the clinic for instructional purposes. Subjects are to apply the study drug twice daily (morning and evening) to a clean dry face.

Study drug is to be applied topically, to the entire face (forehead, nose, cheeks, and chin) by squeezing approximately ½ inch or slightly more than 1 centimeter long line of gel, onto a finger and spreading the gel over the face, avoiding the skin around the eyes, eyelids and mouth, until the face is completely covered.

Subjects are to be instructed to wash their hands prior to and immediately following study drug application.

Subjects should avoid washing the face or swimming within 2 hours after applying study medication.

Missed doses should be applied, provided there is at least an 8 hour window until the next scheduled dose.

6.6 Treatment Compliance

Treatment compliance will be assessed at each visit using a subject-completed diary and visual inspection of the tubes. Subjects will be given a paper diary at each visit in conjunction with study drug. The subject-completed diary will collect application information for the face. Subjects will be instructed to bring all study medication and diaries to the clinic at the next study visit.

A subject deviating significantly from the assigned dosing regimen will be counseled. All diaries will be maintained as source documentation.

The first and last dates of study drug usage, location and any missed applications will be recorded in the eCRF.

6.7 Study Drug Accountability

The Investigator or designee will be responsible for study drug accountability and records at the site. Study drug accountability records will document the receipt, dispensing and return of study drug and provide a complete account of all used and unused drug product. Study drug accountability records will be reviewed regularly throughout the study by the Sponsor/designee. Study medication will be returned to the Sponsor, or designee, at the end of the study, following final study drug accountability.

7 CONCOMITANT MEDICATIONS AND PROCEDURES

All medications (including over-the-counter drugs, vitamins, antacids and skin care products) taken during screening and throughout the study will be recorded on the eCRF. In addition, to ensure that the subject meets the acne treatment and medication exclusion criteria, all acne treatment and medications, including, any past isotretinoin, facial procedures, Vitamin A and hormonal therapy use will be recorded on the eCRF.

Medication entries should be specific to the generic name (if a combination drug, then marketed product name) and will include the dose, unit, frequency, route of administration, start date, discontinuation date, and indication. When listing medications indicated for acne, the area treated will be collected.

The Investigator should examine the acceptability of all concomitant procedures, medications, topical preparations and dietary supplements not explicitly prohibited in this study. In order to ensure that appropriate concomitant therapy is administered, subjects will be instructed to consult with the Investigator prior to taking any medication (either self-administered non-prescription drugs or prescription therapy prescribed by another physician).

7.1 Permitted Treatments and Procedures

The use of concomitant medications for medical conditions (e.g., hypertension, diabetes, acute infections) or treatment of an adverse event is permitted during this study as long as medications are not explicitly prohibited by the protocol.

Non-medicated moisturizers and make-up may be used during study participation, provided application occurs after study medication is applied. On study visit days, non-medicated moisturizers and make-up must be removed prior to each study visit as instructed by the Investigator. Subjects' skin care regimen should remain stable/unchanged during study participation.

Non-medicated moisturizers, soaps, and make-up do not need to be recorded as concomitant medications.

7.2 Prohibited Treatments and Procedures

Subjects should not undergo any elective medical procedure without prior consultation with the Investigator. Elective out-patient procedures (e.g., minor outpatient surgery) that might require

hospitalization or anesthesia should be deferred until after the study, whenever clinically appropriate. However, subjects may continue in the study if not contraindicated by the procedure and if continuation is deemed in the subject's best interest.

The following medications and treatments are prohibited during the study:

- Over-the-counter topical medications for acne vulgaris including benzoyl peroxide, topical anti-inflammatory medications, corticosteroids, α-hydroxy/glycolic acid
- Systemically absorbed anti-acne drugs
- Systemic corticosteroids (use of intranasal and inhaled corticosteroids allowed for seasonal allergies and asthma)
- Systemic antibiotics (except in the case of acute medical need to treat infections)
- Prescription topical retinoid use(e.g., tretinoin, tazarotene, adapalene)
- New hormonal therapy or dose change to existing hormonal therapy. Hormonal therapies
 include, but are not limited to, estrogenic and progestational agents such as birth control
 pills.
- Use of androgen receptor blockers (such as spironolactone or flutamide)
- Oral retinoid use (e.g., isotretinoin) or vitamin A supplements greater than 10,000 units/day
- Facial procedures (chemical or laser peel, microdermabrasion, etc.)
- Sun exposure which in the opinion of the investigator could affect the course of acne or any tanning booth use

8 STUDY PROCEDURES

The procedures required for subject evaluation at each study visit are outlined below and in the study Schedule of Visits and Procedures (see Appendix 1). The timing of each study day is relative to the day of initial dosing (Baseline/Day 1). Visit windows are provided to allow study sites some flexibility in maintaining the study visit schedule for participating subjects. Out of window visits may be unavoidable in certain circumstances. Out of window visits are not considered deviations to the protocol.

8.1 Screening (Day -35 to -1)

The screening evaluation period may take up to 35 days in order to provide adequate washout time for subjects taking certain medications. The purpose of the screening visit is to ensure that appropriate subjects are entered into the study and remain stable during the pre-treatment period. Questions on eligibility will be referred to the Sponsor or their designee. Screen failures may be re-screened one time and must be assigned a new screening number. Screen failure information will be recorded in the eCRF. Screening procedures, excluding lab evaluations, may be done any time during the screening period (prior to dosing on Day 1) and after the subject has given informed consent.

- Obtain written informed consent/assent. For subjects under legal adult age, both parents or legal representatives may be required to sign informed consent as applicable.
- Collect demographic information
- Complete medical history
- Query subject for concomitant medication use
- Perform a complete physical examination
- Record height and weight
- Measure vital signs
- Assess Inclusion/Exclusion criteria
- Collect a 12 lead ECG
- Draw blood samples for laboratory tests and urine for urinalysis. Include serum pregnancy test for women of childbearing potential
- Determine concomitant medication washout duration
- Schedule next visit

8.2 Baseline Visit/ Day 1

Evaluations are to be done prior to the first dose of study drug

- Collect concomitant medication information
- Conduct a symptom-directed physical exam update medical history if appropriate
- Measure vital signs
- Conduct urine pregnancy test for women of childbearing potential
- Conduct Investigator Global Assessment (IGA)
- Collect acne lesion counts
- Collect Acne Patient Self- Questionnaire
- Evaluate face for pre-treatment local skin reactions (LSRs)
- Collect photographs (selected sites)
- Confirm subject eligibility (Inclusion/Exclusion criteria) and randomization to treatment
- Instruct subject on study medication application and diary completion
- Weigh tubes and dispense study drug and diary. Observe subject administering first dose
- Schedule all subsequent visits

8.3 Week 1 (+/-2 days)

- Collect concomitant medication information
- Conduct a symptom-directed physical exam
- Measure vital signs
- Review and record AEs
- Assess LSRs
- Review compliance/weigh tubes and dispense drug and diary
- Schedule Week 2 Telephone Contact and next visit

8.4 Week 2 Telephone Contact (+/-2 days)

• Call subject to review AEs and concomitant medications

8.5 Week 4 (+/-4 days)

- Collect concomitant medication information
- Conduct a symptom-directed physical exam
- Collect urine pregnancy for women of childbearing potential
- Measure vital signs
- Review and record AEs
- Conduct IGA
- Collect acne lesion counts
- Collect Acne Patient Self-Questionnaire
- Assess LSRs
- Collect photographs (selected sites)
- Review compliance/weigh tubes and dispense drug and diary

8.6 Week 8 (+/-4 days)

- Collect concomitant medication information
- Conduct a symptom-directed physical exam
- Collect urine pregnancy for women of childbearing potential
- Measure vital signs
- Review and record AEs
- Conduct IGA

- Collect acne lesion counts
- Collect Acne Patient Self-Questionnaire
- Assess LSRs
- Collect photographs (selected sites)
- Review compliance/weigh tubes and dispense drug and diary

8.7 Week 12 (+/-4 days) Study Exit or Early Termination Visit

- Collect concomitant medication information
- Measure vital signs
- Review and record AEs
- Conduct a complete physical exam
- Measure weight
- Collect a 12-lead ECG
- Draw blood samples for laboratory tests. Include serum pregnancy test for women of childbearing potential.
- Conduct Investigator Global Assessment
- Conduct acne lesion counts
- Collect Acne Patient Self-Questionnaire
- Assess LSRs
- Collect photographs (selected sites)
- Review compliance/weigh tubes and collect all study medication and diary

8.8 Unscheduled Visits

Additional visits may be scheduled as necessary to ensure the safety and well-being of subjects who experience AEs. Laboratory evaluations, if necessary, will be collected and analyzed using the central laboratory for this study. Data will be recorded in the eCRF.

9 DETAILS OF ASSESSMENTS

Parental assistance for study drug application and study conduct procedures may be needed for younger subjects qualifying for study participation.

9.1 Screening Assessments

9.1.1 Demographics

At the screening visit, demographic information including age, gender, race, Fitzpatrick Skin Type (Table 1) and ethnicity will be collected and recorded on the eCRF for each subject.

Table 1: Fitzpatrick Skin Type

Fitzpatrick Skin Type	Definition	
I	Burns easily, rarely tans	
II Burns easily, tans minimally		
III Burns moderately, tans gradually		
IV	Burns minimally, tans well	
V	Rarely burns, tans profusely	
VI	Never burns, deeply pigmented	

9.1.2 Medical History

A complete medical history will be collected as part of the screening assessment and include all clinically relevant past or coexisting medical conditions or surgeries. The medical history will be updated prior to treatment on Baseline/Day 1, should new findings emerge after the screening visit. Findings will be recorded in the eCRF.

9.1.3 Disease Specific Information

Information on the subject's acne vulgaris will be collected as part of the screening assessment and include the date of onset of acne, anatomical areas affected at baseline, and past treatments used for acne vulgaris. Information will be recorded in the eCRF.

9.2 Assessment of Efficacy

9.2.1 Investigator Global Assessment

The IGA is a static assessment of acne severity (Table 2) on the face only and will be conducted for each subject by the Investigator or designee prior to assessing lesion counts or conducting the LSR assessment. Where possible, the same efficacy assessor should assess acne severity on the same subject at all visits. Individuals performing the IGA will be trained and certified prior to conducting any assessments on the study. IGA grades will be entered into the eCRF.

Table 2: Investigator Global Assessment

Investigator Global Assessment			
Grade	Description		
0	Clear; normal, clear skin with no evidence of acne vulgaris		
1	Almost clear; Rare non-inflammatory lesions present, with rare non-inflamed papules (papules must be resolving and may be hyperpigmented, though not pink-red)		
2	Mild; some non-inflammatory lesions are present, with few inflammatory lesions (papules/pustu only; no nodulocystic lesions)		
Moderate; non-inflammatory lesions predominate, with multiple inflammatory lesions evident several to many comedones and papules/pustules, and there may or may not be one small nodulocystic lesions			
Severe; Inflammatory lesions are more apparent, many comedones and papules/pustules, there or may not be a few nodulocystic lesions			

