9.2.2 Acne Lesion Count

The investigator/designee will perform a count of inflammatory lesions (papules, pustules and nodules) and non-inflammatory lesions (open and closed comedones) and will be conducted after the IGA assessment is completed. Lesion counts are confined to the face (including forehead, nose, cheeks, and chin) and exclude submental lesions. Where possible, the same efficacy assessor should perform all lesion count assessments on the same subject at all visits. Individuals performing the acne lesion counts will be trained and certified prior to conducting any assessments on the study. Lesion counts will be entered into the eCRF.

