9.3.2 Acne Patient Self-Questionnaire

Subjects will be asked to complete Acne Patient Self-Questionnaire. The questionnaire is paper-based and will be completed by subjects during clinic visits (see Appendix 2). Subject responses will be entered in the eCRF by the study site and the completed questionnaires kept as part of the subject's source document. Study site staff must review all forms to ensure complete responses prior to a subject leaving the study site.

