9.4.5 Local Skin Reactions (LSRs)

All subjects will be assessed for LSRs, on the face, at each visit. LSRs include burning/stinging, pruritus, erythema, dryness and peeling. Each LSR will be scored as 0 (None), 1 (Mild), 2 (Moderate) or 3 (Severe). LSRs observed on a visit day will not be recorded as adverse events

unless scored as 3 (Severe). Local skin reactions experienced by the subject in between study visits are to be recorded as an AE.

Burning/stinging and pruritus will be assessed by the subject (Table 3) and erythema, dryness and peeling will be assessed by the Investigator/designee (Table 4). Subjects will be read the definition of each subject-assessed LSR and asked to select the appropriate definition. The corresponding score will be assigned by the site and entered in the eCRF.

Table 3: Subject Assessed Local Skin Reactions

Score	Grade	Burning/Stinging	Pruritus
0	None	No stinging/burning	No pruritus
1	Mild	Slightly warm, tingling sensation; not really bothersome	Occasional, slight itching/scratching
2	Moderate	Definite warm; tingling/stinging sensation that is somewhat bothersome	Intermittent itching/scratching which does not disturb sleep
3	Severe	Hot, tingling/stinging sensation that has caused definite discomfort	Bothersome itching/scratching which disturbs sleep

Table 4: Investigator Assessed Local Skin Reactions

Score	Grade	Erythema	Dryness	Peeling
0	None	None	None	None
1	Mild	Slight erythema: very light- pink	Perceptible dryness with no flakes or fissure formation	Mild diffuse peeling
2	Moderate	Dull red, clearly distinguishable	Easily noted dryness and flakes but no fissure formation	Moderate diffuse peeling
3	Severe	Deep/dark red	Easily noted dryness with flakes and fissure formation	Moderate to prominent, dense peeling

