9.4.6 Adverse Events

An adverse event (AE) is defined as any untoward medical occurrence associated with the use of a study drug in humans, whether or not considered drug related. An AE can, therefore, be any unfavorable and unintended sign (including an abnormal laboratory finding), symptom or disease temporally associated with the use of the study drug, whether or not related to the investigational product.

AEs will be monitored throughout the study. Subjects will be instructed to inform the Investigator and/or study staff of any AEs. At each visit, subjects will be asked about AEs in a non-specific manner using open-ended questions so as not to bias the response (e.g., How have you been since the last visit?). Specific inquiry regarding reported AEs will be conducted when applicable. All AEs will be documented and recorded in the subject's eCRF.

Any subject who has an AE (serious or non-serious) or clinically significant abnormal laboratory test value will be evaluated by the Investigator, and will be treated and/or followed up until the symptoms or values return to normal or to clinically acceptable levels, as judged by the

Investigator. A physician, either at clinical site, or at a nearby hospital emergency room, will administer treatment for any serious adverse events (SAEs), if necessary. When appropriate, medical tests and examinations will be performed to document resolution of event(s).

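### The protocol does not place AE questioning after the IGA and lesion counts, so an assessor who also takes AEs may hear of local skin reactions just before scoring the three co-primaries

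*Protocol*

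**What the plan says.** **Order rules.** Protocol 9.2.1 requires the IGA prior "to assessing lesion counts or conducting the LSR assessment". Protocol 9.2.2 says of the lesion counts that the assessment "will be conducted after the IGA assessment is completed". These are the only written rules on the order of the efficacy scores. Neither refers to AEs, and 9.2.2 does not refer to LSR scoring. The SAP adds no rule; its section 4.1.1 points to Protocol Appendix 1.

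**Where local reactions are recorded.** Protocol 9.4.5 splits them by timing. For the visit day, "LSRs observed on a visit day will not be recorded as adverse events" unless severe. For the time at home, "Local skin reactions experienced by the subject in between study visits are to be recorded as an AE". Section 9.4.6 sets how AEs are elicited: "At each visit, subjects will be asked about AEs in a non-specific manner using open-ended questions so as not to bias the response". Section 9.4.6.1 has the investigator decide whether each AE is related to study drug.

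**Visit lists.** In 8.5, 8.6 and 8.7 the item "Review and record AEs" stands above the IGA and the lesion counts. The questionnaire, LSR assessment, photographs and compliance/tube review stand below both.

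**Who does what.** The IGA, the counts and the investigator-assessed LSRs may each be done by the investigator or a designee. No section requires the efficacy assessor to be someone other than the person taking AEs.

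**The concern.** All three co-primaries are judgements by site staff: two lesion counts and a global grade. The protocol keeps the same-day LSR score away from the IGA, but the same kinds of symptom, if felt at home, reach the site through AE review, which is listed ahead of scoring. An assessor who works down the list and takes AEs personally could hear of burning or itching, and form a view on whether the drug caused it, minutes before grading.

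The protocol itself expects such reactions. Section 1.2 names itching at the application site among the commonest AEs of the dose-ranging study, and 9.4.8 uses itching as its example of an intolerable treatment-related event. If reactions were more frequent in one arm and knowledge of them coloured the scores, the treatment difference would be biased on all three co-primaries. Week 12 matters most, because the primary endpoints are read there.

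**Working it through.** **Text check.** The plan states no figure on this point, so the first step is to set the sections side by side.

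| Score | Before LSR scoring? | Before AE questioning? |
|---|---|---|
| IGA | Yes, by rule (9.2.1) | No rule; listed after it (8.5 to 8.7) |
| Lesion counts | No rule in 9.2.2, but listed before it (8.5 to 8.7) | No rule; listed after it (8.5 to 8.7) |

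On AE questioning, all three co-primaries are in the same position: no rule, and a listed order that puts AEs first. On LSR scoring, the counts lack a written rule but the lists already place them first.

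**Yardsticks from the sample size section** (Protocol 11.14, SAP 4.2): IGA 20.5 − 9.6 = 10.9 points; inflammatory 15.21 − 9.7 = 5.51 lesions (SD 11.00); non-inflammatory 14.73 − 9.70 = 5.03 lesions (SD 16.72). The section's own claims reproduce: 300/150 gives 99.9% power (stated at least 95%), 450/225 gives 95.8% (stated 95%), and the continuity-corrected IGA size is 444/222 as stated.

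**Illustration; every input in this step is assumed.** Let d be the excess proportion of active-arm subjects who report a reaction, and s the shift in score when the assessor knows of it, taken to favour active. If s is the same in both arms, the spurious difference is d × s. For example, 0.10 × 4 lesions = 0.4 lesions, and 0.10 × 20 points = 2.0 points.

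Rejection rates are two-sided at 0.05 per endpoint, with no true drug effect, 467 and 233 subjects, a vehicle IGA success rate of 9.6% and a normal approximation. For a count, SE = SD × √(1/467 + 1/233) = SD × 0.0802, which is 0.88 (inflammatory) or 1.34 (non-inflammatory). The rate is Φ(ds/SE − 1.96) + Φ(−ds/SE − 1.96). At ds = 0.8 for inflammatory lesions, ds/SE = 0.91 and the rate is 14.8%. The IGA uses the corresponding two-proportion test without continuity correction.

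| Excess d | Shift s (lesions / IGA points) | Spurious difference (lesions / IGA points) | Inflammatory | Non-inflammatory | IGA |
|---|---|---|---|---|---|
| 0 | any | 0 / 0 | 5.0% | 5.0% | 5.0% |
| 5 points | 2 / 10 | 0.1 / 0.5 | 5.1% | 5.1% | 5.3% |
| 5 points | 4 / 20 | 0.2 / 1.0 | 5.6% | 5.3% | 6.6% |
| 10 points | 2 / 10 | 0.2 / 1.0 | 5.6% | 5.3% | 6.6% |
| 10 points | 4 / 20 | 0.4 / 2.0 | 7.4% | 6.0% | 11.8% |
| 20 points | 2 / 10 | 0.4 / 2.0 | 7.4% | 6.0% | 11.8% |
| 20 points | 4 / 20 | 0.8 / 4.0 | 14.8% | 9.2% | 32.2% |

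These are per-endpoint rates. A claim that needed all three endpoints would be rejected no more often than the lowest of the three. The table also credits all of the assessor's knowledge to same-day AE review, which overstates what a reordering would remove.

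**The case against.** The strongest reply is that the order of the lists may mean little. Section 8 says: "The procedures required for subject evaluation at each study visit are outlined below and in the study Schedule of Visits and Procedures". That describes an outline, not a sequence. Appendix 1 puts both the AE and the LSR rows above the IGA row, which cannot be procedural order given 9.2.1. This stands: AE review first is permitted and suggested, not required. It does not close the gap, because no rule prevents that order.

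A reader might go further than the documents allow in four ways.

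- **That local reactions reveal the arm.** No by-arm rates are given. Section 6.1 describes a vehicle of the same appearance and the same alcohol base, so reactions could occur in both arms. With no imbalance the illustration gives no bias.
- **That a blinding safeguard is defeated.** Section 9.2.1 gives no reason for the IGA coming first. Because it also precedes the counts, the rule fits equally well with keeping a global grade independent of them. The stated blinding measures are elsewhere: blinded site staff (6.3), a matched vehicle (6.1) and identical tubes (6.2).
- **That the questionnaire and tube review expose the assessor too.** They are listed after both efficacy scores. The questionnaire is completed by the subject on paper, and the staff task is a completeness check: "Study site staff must review all forms to ensure complete responses prior to a subject leaving the study site".
- **That subjects are prompted about skin reactions before grading.** AE questions are open-ended; specific inquiry follows only what the subject reports.

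A further objection is that reordering cannot remove the exposure. AEs and LSRs are collected at Week 1, AEs again at the Week 2 call, and LSRs at Weeks 4 and 8. The same efficacy assessor is preferred throughout, physical examination is also listed before the IGA, and redness or peeling is visible on the face being graded. This stands, and it limits what the fix can claim.

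**Conclusion.** The gap is real but narrow. The protocol neither places AE questioning after the IGA and lesion counts nor assigns it to a different person, and its visit lists show it first. An assessor who also takes AEs may therefore hear, and may judge the relatedness of, local reactions just before scoring.

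Neither the direction nor the size of any bias can be established from the documents. On the assumed inputs above, the spurious difference runs from nothing to 0.8 lesions and 4 points of IGA success. At a 10-point excess it is 0.2 to 0.4 lesions (at most 0.4/5.03 = 8% of the smaller planned lesion difference) and 1 to 2 points of IGA success (at most 2/10.9 = 18% of the planned difference). This rests on an excess of reactions on active, a scoring shift towards active, and the same person doing both tasks; none of these is shown. It is a worthwhile, inexpensive improvement in a confirmatory trial with subjective co-primaries, not evidence that the blind fails.

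**What to change.** - In 9.2.1 and 9.2.2, state that at Weeks 4, 8 and 12/ET the IGA and both lesion counts are completed and recorded before AE questioning and LSR scoring.
- In 8.5, 8.6 and 8.7, move AE review below the IGA and lesion counts.
- Leave the questionnaire and the tube and diary review where they are, after the efficacy scores.
- Add a line on the sequence to the assessor training.

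The cost is protocol wording, the training line and a slightly less flexible visit flow; no extra staff, visits or procedures are needed. The change limits same-day exposure only. It does not remove what the assessor may know from Week 1 and later visits or can see on the face.
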